3.10 Subject Completion or Withdrawal

3.10.1 Study Completion

Once the subject has completed the final 12 month follow-up visit they are to be exited from the study.

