3.11.4 Arrhythmia Core Lab

An Arrhythmia Core Lab will oversee the provision, collection and analysis of data from the Event Monitors and Holter Monitors specified in this protocol.

- An Event Monitor will be provided at the 75-Day Remap to be used through the remainder of the 12-month follow-up interval for weekly scheduled and ad hoc symptomatic monitoring. Investigational sites will be provided with the Event Monitor and instructions for its use by the Arrhythmia Core Lab. The investigational sites will then provide the device and instructions for use to the subject. The Event Monitor will be returned to the Arrhythmia Core Lab at the time of the subject's exit from the study. ECG data from the Event Monitor will be analyzed by the Arrhythmia Core Lab.
- A 24-hour continuous ECG monitor will be provided at the 6 and 12-Month Visits. Investigational sites will be provided with the continuous ECG monitor device and instructions for its use by the Arrhythmia Core Lab. The investigational sites will then provide the device and instructions for use to the subject. The device will be worn by the subject for a single 24-hour period and

then returned to the Core Lab with shipping materials provided by the core lab. ECG data from this monitor will be analyzed by the Core Lab.

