- Heart failure status as assessed by NYHA classification at the time of visit

3.12.7 12-Month Visit

Subjects will return for an office visit 12 months (365 days \pm 30 days) following the Index Procedure. At a minimum, the following data will be collected at the 12-Month Visit:

- Adverse Events

- Symptoms of recurrent arrhythmia
- If either the post-Index Procedure or post-75-Day Remap Procedure fluoroscopies indicated diminished phrenic nerve response, and resolution has not been previously demonstrated, a repeat fluoroscopic examination. Females of childbearing potential undergoing this examination will also receive a pregnancy test prior.
- Data regarding the use, changes in or discontinuation of anticoagulation, rate control and/or antiarrhythmic medications.
- Cardiac rhythm as determined by a 12-lead ECG at the time of the visit
- Arrhythmia assessment (See **Section 3.11.4, Arrhythmia Core Lab**).
 - A 24-hour continuous ECG monitor will be provided to the subject.
 - Instructions for returning the Event Monitor will be provided
- Cardioversions, ablations or hospital admissions since last visit
- Heart failure status as assessed by NYHA classification at the time of visit

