3.13 Schedule of Study Assessments

Table 3. Summary of Study Assessments

Assessment	Baseline	Procedure	Pre-Discharge	30-Days Post-Procedure (± 7 days)	75-Days (± 15 days)	6-Month (180 ± 30 days)	12-Month (365 ± 30 days)	Unscheduled
Medical History, CHA ₂ DS ₂ -VASC	X							
AFD and Anticoagulant Medications	X		X	X	X	X	X	X
Symptoms of recurrent arrhythmia				X	X	X	X	X
History of cardioversions, ablations, hospital admissions since last visit			X	X	X	X	X	X
Pregnancy test (for females of childbearing potential)	X	X			X	X ⁴	X ⁴	
12-lead ECG	X		X	X	X	X	X	X
24-Hour Continuous ECG Monitor (e.g., Holter)						X	X	
Cardiac CT/MRI for LA and PV dimensions	X				X			
Mediastinal MRI			X ¹					
TEE or other imaging modality (to exclude left atrial thrombus)	X							
Electroanatomical Mapping		X			X			
Event Monitor readiness/compliance					X	X	X	X
NIHSS	X		X					
Neurologic exam			X ²					
NYHA Classification	X		X	X	X	X	X	X
Fluoroscopic Examination of Diaphragm		X			X if remapped, X ³ if not	X ³	X ³	
Adverse Events		X	X	X	X	X	X	X

¹ At investigator's discretion

² If NIHSS score has increased by 2 or more points or if clinical suspicion of stroke/TIA

³ If the Index Procedure or Remap Procedure study indicated decreased phrenic nerve function and resolution has not yet been demonstrated.

⁴ As required for females of childbearing potential undergoing fluoroscopic examination of the diaphragm

4. Benefit Risk Assessment

The Sponsor has conducted an analysis of the benefits and risks of the FARAPULSE Endocardial Multi Ablation System and ablation procedure as described below. The conclusion of this review is that the subject investigation is justified because the overall potential benefit to the population outweighs the risks.

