2.1.4. Inferential Analysis

- Confidence intervals:

When applicable, bilateral asymptotic or exact confidence intervals for binomial distributions will be calculated at the 95% level.

For categorical variables, if pertinent, the 95% asymptotic confidence interval will be calculated if theoretical assumptions are verified. If this is not the case, and the corresponding proportion is 0% or 100%, then the Agresti-Coull confidence interval will be calculated instead. In all other cases, the exact confidence interval will be calculated.

- Survival analysis:

Time-to-event variables will be described over time by survival curves as per the Kaplan-Meier method together with the associated estimators, considering the upper window of the corresponding visits. The survival rate will be presented at each time point (30 days, 90 days, 180 days, 365 days) and overall.

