4.3. Graphs

4.3.1. Graph 1: Patient disposition

4.3.2. Graph 2: Freedom from AF/AFL/AT on ADDs

- Summary table

	Group 1 (N=XXX)
Nb of patients	XXX
Nb of patients with an event	XX (XX.X%)
Nb of patients without an event	XX (XX.X%)
Survival rate	XX %
Time to event (days)	
Median	XX
(95% CI)	(XX, XX)
25th-75th percentile	XXX – XXX
Range	X.XX - X.XX

CONFIDENTIEL / CONFIDENTIAL

Toute reproduction ou distribution, totale ou partielle, de ce document, sans autorisation préalable de ICON PLC est interdite.
Reproduction and distribution of this document, in whole or in part, is strictly forbidden without prior authorization from ICON PLC.

	STATISTICAL ANALYSIS PLAN	FARAPULSE PersAFOne SAP V1.0 PERSAFONE Page 49 /49
---	----------------------------------	--

- 4.3.3. Graph 3: Freedom from AF/AFL/AT off ADDs**
- 4.3.4. Graph 4: Freedom from AF on AADs**
- 4.3.5. Graph 5: Freedom from AF off AADs**
- 4.3.6. Graph 6: Freedom from AF/AFL/AT, no DCCV>90 days, no RF, no ablation >90 days**
- 4.3.7. Graph 7: Freedom from AF/AFL/AT, no DCCV>90 days, no RF, no ablation >90 days on AADS**
- 4.3.8. Graph 8: Freedom from AF/AFL/AT, no DCCV>90 days, no RF, no ablation >90 days off AADS**
- 4.3.9. Graph 9: Freedom from AF, no DCCV>90 days, no RF, no ablation >90 days on AADs**
- 4.3.10. Graph 10: Freedom from AF, no DCCV>90 days, no RF, no ablation >90 days off AADs**
- 4.3.11. Graph 11: Death**

CONFIDENTIEL / CONFIDENTIAL

Toute reproduction ou distribution, totale ou partielle, de ce document, sans autorisation préalable de ICON PLC est interdite.
Reproduction and distribution of this document, in whole or in part, is strictly forbidden without prior authorization from ICON PLC.

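### Kaplan-Meier rates read at the upper visit window or at the end of the curve understate 12-month freedom from arrhythmia if month-12 failures and exits keep their actual dates

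*SAP*

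**What the plan says.** SAP 2.1.4 describes time-to-event variables by Kaplan-Meier curves, "considering the upper window of the corresponding visits", and continues: "The survival rate will be presented at each time point (30 days, 90 days, 180 days, 365 days) and overall". These two statements do not fit together. The upper windows in Protocol 3.13, Table 3 are days 37 (30 + 7), 90 (75 + 15), 210 (180 + 30) and 395 (365 + 30). Of the listed days, only 90 is an upper window; 30, 180 and 365 are nominal. So the 12-month rate could be the estimate at day 365 or at day 395, and an overall rate is reported as well.

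Three protocol rules fix when observation ends.
- Section 3.11.4: "A 24-hour continuous ECG monitor will be provided at the 6 and 12-Month Visits". The 12-month visit may fall on any day from 335 to 395.
- Section 3.10.1: "Once the subject has completed the final 12 month follow-up visit they are to be exited from the study".
- Section 3.11.4: "The Event Monitor will be returned to the Arrhythmia Core Lab at the time of the subject's exit from the study".

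The Kaplan-Meier times are day counts supplied in a spreadsheet from the sponsor (SAP, Databases subsection of 2.3). SAP 2.5 does not derive them. It does define a follow-up time, exit date minus procedure date, but does not say that this is the censoring time for the curves.

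Freedom from AF/AFL/AT (Table 7) and Therapeutic Success (Table 13) are n/N proportions. The summary table under Graph 2 (SAP 4.3.2) prints one line, "Survival rate", with no day attached and no number at risk.

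**The concern.** Kaplan-Meier assumes that a subject censored on day 340 would have gone on to face the same risk as those still under observation. That fails here. The subject censored on day 340 has already had the month-12 Holter, and the subjects still at risk have not. Every completer has this one test once, and exits just after it.

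With actual dates, a clean Holter removes a subject from the risk set on his own exit day, and a positive Holter is an event on his own exit day. The later a positive result comes in the order of exit, the fewer subjects it is divided by. Reading the curve at day 395 or at its end collects all of these steps.

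At stake is the survival rate attached to the arrhythmia-freedom graphs. The Graph 2 template would print it beside the percentage of patients without an event, and the two could differ widely only because of visit scheduling. SAP 2.2 says the results will inform later studies.

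**Working it through.** The plan gives no Kaplan-Meier rate, event rate or sample-size calculation, so there is no figure of its own to reproduce.

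**Inputs from the documents.** Month-12 window: 365 − 30 = 335 to 365 + 30 = 395. One Holter per completer at that visit, then exit. N up to 40.

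**Assumptions, because the documents give no rates.** 25% fail on days 91 to 334. A proportion p of the rest fail only on the month-12 Holter (2.5% to 15%). No dropout. Month-12 events and exits carry actual dates.

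**Step 1, closed form.** Let m subjects enter the window on distinct visit days. When k remain at risk, the next Holter multiplies the curve by (1 − 1/k) with probability p and by 1 otherwise, so the expected factor is 1 − p/k. Over the whole window the expected factor is the product of (1 − p/k) for k = 1 to m. The correct factor is 1 − p. For m = 30:

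| p | Expected factor at day 395 | Correct factor |
|---|---|---|
| 2.5% | 0.904 | 0.975 |
| 5% | 0.817 | 0.950 |
| 10% | 0.665 | 0.900 |

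A larger sample does not help. At p = 5% the factor is 0.845 for m = 15 and 0.806 for m = 40. Small groups do not escape either: m = 10 gives 0.862.

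**Step 2, worked example.** Of 40 subjects, 10 fail earlier and 30 reach the visit. The 20th and 28th to exit have positive Holters, with 11 and 3 at risk.
- Kaplan-Meier at day 395: 0.75 × (1 − 1/11) × (1 − 1/3) = 0.455.
- Proportion free: 28/40 = 0.700.

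**Step 3, simulation.** 4,000 trials per row, N = 40, visits uniform on days 335 to 395. Truth is 0.75 × (1 − p). The median shortfall is taken against the same trial's own proportion.

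| p | Truth | Mean KM, day 395 | Mean shortfall, points | Median shortfall, points | Mean KM, day 365 | Mean KM, month-12 outcomes all on day 365 |
|---|---|---|---|---|---|---|
| 2.5% | 0.731 | 0.676 | 5.5 | 0.3 | 0.736 | 0.730 |
| 5% | 0.712 | 0.624 | 8.8 | 3.0 | 0.725 | 0.713 |
| 10% | 0.675 | 0.508 | 16.7 | 10.4 | 0.699 | 0.674 |
| 15% | 0.637 | 0.419 | 21.8 | 17.0 | 0.676 | 0.638 |

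The mean exceeds the median because a few trials go badly wrong. The curve falls to zero in 2.2% to 11.6% of runs, which happens when the last exit has a positive Holter. Visits clustered around day 365 (SD 10 days) give nearly the same values. With N = 25 the day-395 mean runs from 0.686 (p = 2.5%) to 0.437 (p = 15%).

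**Step 4, reading at day 365 with actual dates.** The error reverses: 0.736 − 0.731 = 0.5 points too high at p = 2.5%, rising to 0.676 − 0.637 = 3.9 points at p = 15%. Completers who exited before day 365 have left the risk set, and later Holter failures are not counted.

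**The case against.** The strongest reply is that the result needs each subject's own last day as the Kaplan-Meier time, and neither document says so. The sponsor's variable is undefined, and completers may already be set to one day. The upper-window phrase could even mean that visit outcomes are assigned to the upper window, which would be such a rule. This stands: the point is conditional. But nothing in the SAP prevents actual dating, and the only follow-up time it defines ends on the subject's own exit date.

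The sizes also rest on an assumed p. Weekly and symptomatic event-monitor recordings run until exit and should leave fewer failures for the last Holter to find. If 30 subjects reach the visit, the chance of no Holter-only failure is 0.975^30 = 47% at p = 2.5% and 0.95^30 = 21% at p = 5%. In such trials the effect is absent. This stands too, and is why medians are shown.

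A reader might infer that the trial's reported freedom from arrhythmia is understated in general. The documents do not support that. Tables 7 and 13 are simple proportions, and the day-365 reading errs slightly in the other direction. Nor can the N = 40 figures be carried over to every graph: Graphs 2 to 5 and 7 to 10 are split by drug use into groups of unknown size, and the summary template is shown only under Graph 2.

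Finally, this is a descriptive feasibility study, and no stated decision uses the Kaplan-Meier rate. That limits the consequence but does not make the rate right.

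**Conclusion.** The point holds conditionally and is confined to the Kaplan-Meier graphs and their survival rates. With actual event and exit dates, a curve read at day 395 or at its end understates freedom from arrhythmia. For p of 2.5% to 10%, with 25% failing earlier and N = 40, the mean shortfall is about 6 to 17 points and the median about 0.3 to 10. It is zero if no one fails only on the final Holter, or if failures and completers already share one analysis day. Read at day 365, the rate is about 1 to 4 points too high over the range examined.

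The month-6 Holter does not raise the problem, because subjects stay under observation after it. The correction should be made before the graphs are produced, but it does not bear on the primary endpoints.

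**What to change.** Amend SAP 2.1.4 as follows.
- Define the event date and the censoring date for each Kaplan-Meier variable, including those taken from the sponsor's spreadsheet.
- For subjects with a completed month-12 visit or Holter, place failures found there and event-free censoring on one common day, 365, with events ordered before censorings.
- Censor subjects who withdraw or are lost without that visit on their actual last day. A rule that moved everyone followed to day 335 or later would wrongly count a withdrawal on day 336 as a completed 12-month assessment.
- State that the 12-month rate is the day-365 estimate, drop the overall rate, and print numbers at risk.

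In the simulation without dropout, the common day reproduces the proportion free. The cost is a few sentences in the SAP and a short change to the program. The downside is that event times in the last window become nominal rather than exact.

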2.1.5. Data Listings

Patient data listings will be selected data supportive of summary statistical tables, including derived/calculated data from statistical process. These data listings are performed on selected analysis sets according to the focus of the analysis and are sorted by subject number and visit. Data entry into a free field in the CRF will be described in the listings.

2.2. Sample size calculation

This investigation is the next phase of ongoing feasibility studies to allow the controlled introduction of a new cardiac ablation catheter (FARAFLEX Endocardial Ablation Catheter). This is a feasibility study with no formal hypothesis testing and therefore no required sample size. Study results will be presented using descriptive statistics. Results from this study will be used to inform and design additional clinical studies.

Forty (40) subjects at up to four sites will allow the assessment of the modified devices and the initial experience and training of investigators and study staff at a new investigational site.

CONFIDENTIEL / CONFIDENTIAL

Toute reproduction ou distribution, totale ou partielle, de ce document, sans autorisation préalable de ICON PLC est interdite.
Reproduction and distribution of this document, in whole or in part, is strictly forbidden without prior authorization from ICON PLC.

	STATISTICAL ANALYSIS PLAN	FARAPULSE PersAFOne SAP V1.0 PERSAFONE Page 14 /49
---	----------------------------------	--

2.3. Analysis Sets

2.3.1. Definition of patient populations

3 populations will be defined:

- The Enrolled population will include all subjects who provided their informed consent.
- The Safety / Intent-to-Treat (ITT) population will include all enrolled subjects except those who terminate their participation prior to the beginning of the Index Procedure.
- The Per Protocol (PP) population will include Intent-to-treat subjects for whom the Index Procedure is finished without interfering investigational device deficiency or malfunction.

The choice of reported analysis on ITT or PP populations will be driven by the purposes of the analysis.

In any case, the primary feasibility endpoint will be assessed on the ITT and PP populations.

2.3.2. Protocol Deviations

On a case-by-case basis, all protocol deviations will be reviewed and classified as "Related to COVID-19 situation (type9)" or "Not related to COVID-19 situation (type9)".

Deviation types:

- Consentement inappropriately obtained
- Procedure not performed according to protocol/IFU
- Inclusion/Exclusion Criteria deviation
- Protocol required test not completed
- Missed Follow-up visit
- Follow-up visit performed outside of window
- Other
- Related to COVID-19 situation

2.3.1. Databases

The Remapping at 75 Days, recurrence and Additional endpoints analysis will be based on the MDT Excel file sent by sponsor, which will contain:

- Received ablation at remap"
- RF/PFA ablation at remap
- Early recurrence of atrial fibrillation (AF)
- AF status
- AF km days"
- Atrial fibrillation/ Atrial flutter / Atrial tachycardia (AF/AFL/AT) status"
- AF/AFL/AT km (days)
- Transtelephonic monitor (TTM) weeks expected
- TTM weeks received
- Number TTM transmissions
- 6-month holter
- 12-month holter
- Radiofrequency (RF) touchup

CONFIDENTIEL / CONFIDENTIAL

Toute reproduction ou distribution, totale ou partielle, de ce document, sans autorisation préalable de ICON PLC est interdite.
Reproduction and distribution of this document, in whole or in part, is strictly forbidden without prior authorization from ICON PLC.

	STATISTICAL ANALYSIS PLAN	FARAPULSE PersAFOne SAP V1.0 PERSAFONE Page 15 /49
---	----------------------------------	--

- Ablation (ABL) >90 days"
- Class I/III antiarrhythmics drug (AAD) >90 days
- Amiodarone
- Direct current cardioversion (DCCV) >90 days
- Arrhythmia-related (AF, AFL, AT) hospitalization

The Excel file sent by the Sponsor will have the same structure (in terms of variables names, labels, formats) for each analysis to ensure the continuity of the programming.

All other analysis will be done on the e-CRF clinical database.

2.4. Statistical Analyses

2.4.1. Patient Disposition and Follow-up

2.4.1.1. *Patient Populations Sample Size*

The number and percentage of patients included in each population and the reasons of non-inclusion in each subsequent population will be presented on the enrolled population.

The number and percentage of patients present at each visit will be presented with the study exit reasons.

A listing will be provided to present patient disposition. The following variables will be listed:

- Date of consent
- Procedure date
- Remap date
- Most recent follow-up
- Date of study exit
- Follow up time (days)

2.4.1.2. *Protocol Deviations*

Frequency of patients with at least one protocol deviation, as well as the total number of events, will be summarized on the ITT population, by Type of deviation in relation with COVID status.

The detail will be also presented in a listing.

2.4.2. Baseline Patient Characteristics

Descriptive statistical data will be used to draw up a recapitulation of the characteristics of the patients at the time of enrolment. It will be summarized on the ITT population.

- Demographics at baseline: Age, Gender, BMI
- Baseline Medical History : LA diameter, Time from first AF diagnosis until consent date, Patient failed at least one AAD, Class of AAD if Yes, Left Ventricular Ejection Fraction (LVEF) (%), CHA2DS2-VASc Score, Smoking, Dyslipidemia, Chronic Obstructive Pulmonary Disease, Permanent pacemaker or ICD, Unstable angina, NYHA class, Structural Heart Disease and Type(s) if yes, Cerebrovascular disease and Type, Cardiac surgery and type if yes, Diabetes, Hypertension, Hyperthyroidism,

CONFIDENTIEL / CONFIDENTIAL

	STATISTICAL ANALYSIS PLAN	FARAPULSE PersAFOne SAP V1.0 PERSAFONE Page 16 /49
---	----------------------------------	--

Hypothyroidism, Myocardial infarction, Peripheral vascular disease, Pulmonary hypertension, Renal dysfunction/failure, Sleep apnea.

A listing will be provided to present previous parameter as well as: Pregnancy test, height, weight, Heart rate; Systolic and diastolic blood pressure, heart rate, Time between the most recent AF episode and the enrollment (months), Name and dose of ADD failed drug.

2.4.3. Index Procedure

Descriptive statistical data will be used to draw up a recapitulation of the intervention details at the time of the procedure.

The following data will be presented on the ITT population:

- Procedure Data: Procedure time, Farawave dwell total time, PVI ablation time, CTI (FARAFLEX) dwell time, LAPW ablation time (LAST LAPW ablation - FIRST LAPW ablation), Fluoroscopy time, Total amount of contrast dye injected (contrast volume (cc)), Total volume of IV fluids administered (IV fluid volume (cc)), Total number of PVI applications, Number of PVI ablation/patient, Number of applications/vein, Number of LAPW applications, Total number of veins treated, Total number of veins isolated, Of the total number of veins treated, the number of veins isolated (Proportion of veins isolated), CTI acute isolation, Total number of CTI applications.

2.4.4. Remapping at 75 Days

Descriptive statistical data will be used to draw up a recapitulation of the follow-up details at 75-day Visit and Remapping Procedure.

The following data will be presented on the ITT population:

Days follow up at remap, Durable PVI, LSPV chronic isolation, LIPV chronic isolation, LCPV chronic isolation, RSPV chronic isolation, RIPV chronic isolation, RMPV chronic isolation, CTI chronic isolation, LAPW chronic isolation, Number of veins durably isolated, Number of veins with gaps.

2.4.5. 6 and 12 Months follow up

Descriptive statistical data will be used to draw up a recapitulation of the follow-up details at 6 and 12 Months follow up.

The following data will be presented on the ITT population:

TTM compliance, Holter compliance (6 month and 12 month), Freedom from AF/AFL/AT (for patient On AADs and on patient Off AADs), Freedom from AF (for patient On AADs and on patient Off AADs), Freedom from AF/AFL/AT, no DCCV>90 days, no RF, no ablation >90 days (for patient On AADs and on patient Off AADs), Freedom from AF, no DCCV>90 days, no RF, no ablation >90 days (for patient On AADs and on patient Off AADs).

